4.2.2. Main analytical approach

4.2.2.1. Long-term follow-up phase

For persistence of humoral immunity measured after the primary vaccination course, the following parameters will be tabulated. ZOSTER-073 Day 1, study Month 12 and study Month 24 measurements will be displayed in tables and figures in terms of time since primary series in ZOSTER-041, grouped into 1 year intervals.

- GMCs of anti-gE antibody, MGI of post-vaccination timepoint over ZOSTER-041 pre-vaccination timepoint, and anti-gE antibody seropositivity rates with 95% CI;
 - GMCs of anti-gE antibody, MGI of post-vaccination timepoint over ZOSTER-041 pre-vaccination timepoint, and anti-gE antibody seropositivity rates with 95% CI will also be presented with Visit 1, Visit 2, and Visit 3 in the LTFU phase of ZOSTER-073 presented as Day 1, Month 12, and Month 24, in accordance to the primary endpoint timepoints.

- Descriptive statistics on anti-gE antibody concentrations (mean, SD, min, Q1, median, Q3, max);
- Vaccine response rates and 95% CIs to ZOSTER-041 pre-primary vaccination for anti-gE antibody concentrations;
- Descriptive statistics of the fold increase of post-vaccination timepoint over ZOSTER-041 pre-vaccination timepoint at ZOSTER-073 Day 1, study Month 12, and study Month 24 (mean, SD, min, Q1, median, Q3, max);
- Distribution of the fold over ZOSTER-041 pre-vaccination timepoint;
- The distribution of antibody titers will be tabulated and also presented using reverse cumulative curves.

Displays of GMCs of anti-gE antibody concentrations will also include all of the ZOSTER-041 timepoints.

Anti-gE antibody concentrations will be displayed graphically by time since primary vaccination dose 2. Values taken pre-primary vaccination, at 1 month post primary vaccination dose-1, and timepoints post-dose 2 of primary vaccination will be presented in separate symbols and colors in the figure, along with a trend line through post-dose 2 points. A line representing the median pre-vaccination concentration will be displayed for comparison.

4.2.2.2. Revaccination active phase

For humoral immunity after revaccination for the active phase, the following parameters will be tabulated. ZOSTER-073 study Months 24, 25, and 26 (Visits 3-5), will be presented as pre-revaccination, 1 month post-revaccination Dose 1, and 1 month post-revaccination Dose 2 in displays.

- GMCs of anti-gE antibody and anti-gE antibody seropositivity rates with 95% CI at pre-revaccination, 1 month post-revaccination Dose 1, and 1 month post-revaccination Dose 2;
- Vaccine response rates for anti-gE antibody concentrations at 1 month post-revaccination Dose 1 and 1 month post-revaccination Dose 2 [post-revaccination timepoint over pre-revaccination timepoint] with 95% CI;
- Vaccine response rates to ZOSTER-041 pre-primary vaccination for anti-gE antibody concentrations at 1 month post-revaccination Dose 1 and 1 month post-revaccination Dose 2 with 95% CI;
- MGI post-revaccination timepoint over pre-revaccination timepoint at 1 month post-revaccination Dose 1 and 1 month post-revaccination Dose 2 with 95% CI;
- MGI post-revaccination timepoint over ZOSTER-041 pre-vaccination timepoint at pre-revaccination, 1 month post-revaccination Dose 1, and 1 month post-revaccination Dose 2 with 95% CI;
- Descriptive statistics of the fold increase of anti-gE antibody concentrations 1 month post-revaccination Dose 1 and 1 month post-revaccination Dose 2 over pre-revaccination timepoint (mean, SD, min, Q1, median, Q3, max).

- Distribution of antibody titers at pre-revaccination, 1 month post-revaccination Dose 1, and 1 month post-revaccination Dose 2 will be tabulated and also presented using reverse cumulative curves.
- Boxplots of anti-gE antibody concentrations will be displayed by visit.

4.3. Secondary Endpoints Analyses

4.3.1. Secondary immunogenicity endpoints

The secondary immunogenicity analyses will use the same analysis sets as described in Section [4.2](#).

4.3.1.1. Definition of endpoints

Refer to Section [4.2.1](#).

4.3.1.2. Main analytical approach

4.3.1.2.1. Long-term follow-up phase

For persistence of cellular immunity after the primary vaccination course as determined by ICS, the following parameters will be tabulated. ZOSTER-073 Day 1, study Month 12 and study Month 24 measurements will be displayed in tables and figures in terms of time since primary series in ZOSTER-041, grouped into 1 year intervals.

- Descriptive statistics (N, mean, SD, min, Q1, median, Q3, max):
 - the frequency of gE specific CD4+T-cells secreting at least 2 activation markers (among IFN- γ , IL-2, TNF- α , CD40L);
 - the fold increase over ZOSTER-041 pre-vaccination timepoint for the frequency of gE-specific CD4(2+) T-cells;
- Vaccine response rates to ZOSTER-041 primary vaccination for frequency of gE-specific CD4(2+) T-cells will be tabulated with 95% CI.

CD4+T-cells secreting at least 2 activation markers will be displayed graphically by time since primary vaccination dose 2. Values taken pre-primary vaccination and post-dose 2 of primary vaccination will be presented in separate symbols and colors in the figure, along with a trend line through post-dose 2 points. A line representing the median pre-vaccination concentration will be displayed for comparison.

4.3.1.2.2. Revaccination active phase

For cellular immunity after revaccination as determined by ICS for the active phase, the following parameters will be tabulated. ZOSTER-073 study Months 24, 25 and 26 (Visits 3-5), will be presented as pre-revaccination, 1 month post-revaccination Dose 1, and 1 month post-revaccination Dose 2 in displays.

- Descriptive statistics (N, mean, SD, min, Q1, median, Q3, max):
 - the frequency of gE specific CD4+T-cells secreting at least 2 activation markers (among IFN- γ , IL-2, TNF- α , CD40L) at pre-revaccination, 1 month post-revaccination Dose 1, and 1 month post-revaccination Dose 2;
 - the fold increase over pre-revaccination timepoint Month 24 in the frequency of gE specific CD4[2+] T-cells at 1 month post-revaccination Dose 1 and 1 month post-revaccination Dose 2.
 - the fold increase over ZOSTER-041 pre-vaccination timepoint in the frequency of gE specific CD4[2+] T-cells at pre-revaccination, 1 month post-revaccination Dose 1, and 1 month post-revaccination Dose 2.
- Vaccine response rates for frequency of gE-specific CD4(2+) T-cells at 1 month post-revaccination Dose 1 and 1 month post-revaccination Dose 2 over pre-revaccination timepoint Month 24 will be tabulated with 95% CI.
- Vaccine response rates to ZOSTER-041 primary vaccination for frequency of gE-specific CD4(2+) T-cells at pre-revaccination, 1 month post-revaccination Dose 1, and 1 month post-revaccination Dose 2 will be tabulated with 95% CI.

CD4+T-cells secreting at least 2 activation markers will also be displayed graphically by timepoint.

4.3.1.2.3. Revaccination follow-up phase

For **humoral immunity** after revaccination (revaccination follow-up phase), the following parameters will be tabulated. ZOSTER-073 study Months 37 and 49 (Visit 6 and Visit 7) data will be presented in terms of time since revaccination, grouped in appropriate month intervals, based on the distribution subjects' visit occurrence. For non-revaccinated subjects, separate summaries will be provided, and data will be presented on time since primary vaccination in ZOSTER-041.

- GMC of anti-gE antibody and anti-gE seropositivity rates with 95%;
- Vaccine response rates for anti-gE antibody concentrations over pre-revaccination timepoint with 95% CI;
- Vaccine response rates to ZOSTER-041 pre-primary vaccination for anti-gE antibody concentrations with 95% CI;
- MGI post-revaccination over pre-revaccination timepoint with 95% CI;
- MGI post-revaccination over ZOSTER-041 pre-vaccination timepoint with 95% CI
- MGI post-revaccination dose 1 over 1 month post primary vaccination dose 2 with 95% CI
- Descriptive statistics of the fold increase of anti-gE antibody concentrations over pre-revaccination timepoint (mean, standard deviation, min, Q1, median, Q3, max).

- Descriptive statistics of the fold increase of anti-gE antibody concentrations over ZOSTER-041 pre-vaccination timepoint (mean, SD, min, Q1, median, Q3, max).
- Distribution of antibody titers will be tabulated and also presented using reverse cumulative curves.
- Boxplots of anti-gE antibody concentrations will be displayed by visit.

For **cellular immunity** after revaccination (revaccination follow-up phase) as determined by ICS, the following parameters will be tabulated. ZOSTER-073 study Months 37 and 49 (Visit 6 and Visit 7) data will be presented in terms of time since revaccination, grouped in appropriate month intervals, based on the distribution subjects' visit occurrence. For non-revaccinated subjects, separate summaries will be provided, and data will be presented on time since primary vaccination in ZOSTER-041.

- Descriptive statistics (N, mean, SD, min, Q1, median, Q3, max):
 - the frequency of gE specific CD4+T-cells secreting at least 2 activation markers (among IFN- γ , IL-2, TNF- α , CD40L);
 - the fold increase over pre-revaccination timepoint in the frequency of gE specific CD4[2+] T-cells.
- Vaccine response rates for frequency of gE-specific CD4(2+) T-cells over pre-revaccination timepoint will be tabulated with 95% CI. Vaccine response rate is defined in Section 6.2.6.4.

4.3.2. Secondary safety endpoints

Safety analyses will be performed on the Enrolled Set for the LTFU phase and the ES for the revaccination phase. All analyses of solicited and unsolicited AEs will be performed overall and by age stratum (based on age at the time of primary vaccination in ZOSTER-041 for the LTFU phase, based on age at the time of revaccination in ZOSTER-073 for revaccination active and follow-up phases).

If the number of subjects with the particular AE is too small (less than [10%] of the sample size), the safety table may not be provided by age stratum.

For solicited AE summaries, the denominators used for deriving percentages will include all revaccinated subjects with at least one solicited local or solicited general symptom documented as either present or absent.

4.3.2.1. Long-term follow-up phase

The results for the analysis of safety in the long-term follow-up phase will be tabulated as follows:

- Number and percentage of subjects reporting at least one SAE related to primary vaccination in study ZOSTER-041 classified by Medical Dictionary for Regulatory Activities (MedDRA) Primary System Organ Class (SOC) and Preferred Term (PT) from the day after

ZOSTER-041 last study visit (Month 13) to ZOSTER-073 pre-revaccination (Visit 3 Month 24) will be tabulated with exact 95% CI.

- Number and percentage of subjects with at least one suspected or biopsy-proven allograft rejection from ZOSTER-041 last visit (Month 13) to ZOSTER-073 Day 1 will be tabulated with exact 95% CI.
- Number and percentage of subjects with at least one biopsy-proven allograft rejection from ZOSTER-073 Day 1 to ZOSTER-073 pre-revaccination (Visit 3 Month 24) will be tabulated with exact 95% CI.
- Number and percentage of subjects with suspected or confirmed HZ cases from ZOSTER-041 last visit (Month 13) to study ZOSTER-073 Day 1 will be tabulated with exact 95% CI.
- Number and percentage of subjects with confirmed HZ cases from ZOSTER-073 Day 1 through ZOSTER-073 study Month 24 will be tabulated with exact 95% CI.
- Listing of subjects with history of suspected allograft rejection or history of biopsy-proven allograft rejections from ZOSTER-041 last study visit to ZOSTER-073 Day 1 will be provided.
- Listing of subjects with biopsy-proven allograft rejections from ZOSTER-073 Day 1 onward will be provided.
- Listing of subjects with a suspected or confirmed HZ episode from ZOSTER-041 last study visit to ZOSTER-073 Day 1 will be provided.
- Listing of subjects with a confirmed HZ episode from ZOSTER-073 Day 1 onward will be provided.
- Number of subjects with declining allograft function (following HZ and allograft rejection episodes), as determined by fold change from baseline serum creatinine measurements, for the time period from study ZOSTER-041 last visit (Month 13) to study ZOSTER-073 Visit 3 (Month 24). This serum creatinine fold change from baseline will be summarized descriptively. A list of subjects with an increase in serum creatinine will also be presented. Allograft dysfunction is defined as having a fold increase in serum creatinine of 1.2 or greater from the reference timepoint.

4.3.2.2. Revaccination phase

The results for the analysis of safety in the revaccination phase will be tabulated as follows:

- Number and percentage of subjects with at least one local AE (solicited and unsolicited), with at least one general AE (solicited and unsolicited), and with any AEs during the solicited 7-day follow-up period will be tabulated with exact 95% CI after each revaccination dose and overall. The same computations will be done for Grade 3 AEs and medically attended AEs. Number and percentage of subjects reporting each individual solicited local AE (any grade and Grade 3) and solicited general AE (any grade, Grade 3, any related and Grade 3 related) during the 7-day follow-up period (i.e., on the day of

[figure not shown]
revaccination and 6 subsequent days) will be tabulated after each revaccination dose and overall.

- Duration of solicited local and solicited general AEs within 7 days and entire duration (lasting longer than 7 days) will be tabulated descriptively overall.
- Number and percentage of subjects with any unsolicited AEs during the 30-day follow-up period (i.e., on the day of revaccination and 29 subsequent days) with its exact 95% CI will be tabulated by MedDRA Primary SOC and PT. Similar tabulations will be done for Grade 3 unsolicited AEs, for any causally related unsolicited AEs, for Grade 3 causally related unsolicited AEs, for Grade 3 non-serious unsolicited AEs, for Grade 3 causally related non-serious unsolicited AEs, non-serious unsolicited AEs, non-serious causally related unsolicited AEs, and for unsolicited AEs resulting in a medically attended visit.
 - The number and percentage doses followed by unsolicited AEs during the 30-day follow-up period with its exact 95% CI will also be tabulated.
- Number and percentage of subjects with at least one report of SAE classified by MedDRA Primary SOC and PT and reported from revaccination Dose 1 up to 30 days post-last revaccination dose, from revaccination Dose 1 up to 12 months post- last revaccination dose, and from revaccination Dose 1 up to study end will be tabulated with exact 95% CI.
- Number and percentage of subjects with at least one report of causally related-SAE classified by MedDRA Primary SOC and PT and reported from revaccination Dose 1 up to 30 days post-last revaccination dose, from revaccination Dose 1 up to 12 months post-last revaccination dose, and from revaccination Dose 1 up to study end will be tabulated with exact 95% CI.
- Number and percentage of subjects with at least one pIMD classified by MedDRA Primary SOC and PT and percentage of subjects with at least one pIMD with causal relationship, reported from revaccination Dose 1 up to 30 days, from revaccination Dose 1 up to 12 months post-last revaccination dose, and from revaccination Dose 1 up to study end will be tabulated with exact 95% CI.
- Number and percentage of subjects with at least one biopsy-proven allograft rejection and biopsy-proven allograft rejection with causal relationship reported from revaccination Dose 1 up to study end will be tabulated with exact 95% CI.
- Number and percentage of subjects with at least one biopsy-proven allograft rejection and biopsy-proven allograft rejection with causal relationship reported from revaccination Dose 1 up to 12 months post last revaccination will be tabulated with exact 95% CI.
- Number and percentage of subjects with fatal SAEs and causally related fatal SAEs classified by MedDRA Primary SOC and PT will be presented. Fatal SAEs and related fatal SAEs will also be described by onset date of SAE and date of death as follows:
 - With onset date of fatal SAE during the period starting from revaccination Dose 1 to 30 days post last revaccination dose, from revaccination Dose 1 up to 12 months post last revaccination, and from revaccination Dose 1 up to study end

[figure not shown]
- Who died (date of death) during the period starting from revaccination Dose 1 up to 30 days post last revaccination dose, from revaccination Dose 1 up to 12 months post last revaccination, and from first revaccination to study end.
- SAEs and pIMDs will be listed. These listings will include all fields on the CRF, including but not limited to, verbatim event description, MedDRA SOC/PT, start/stop study days, site, intensity (maximum and at time of onset), relationship to study vaccine, outcome.
- Listing of withdrawals due to AE and SAEs will be provided, including verbatim event description, MedDRA SOC/PT, start/stop study days, site, intensity (maximum and at time of onset), relationship to study vaccine, outcome
- Listing of subjects with confirmed HZ episode from Dose 1 of revaccination (Month 24) up to study end will be provided.
- Listing of subjects with biopsy-proven allograft rejection from Dose 1 of revaccination (study Month 24) up to study end will be provided. For subjects with an episode of biopsy-proven rejection, dates of biopsy-proven rejection episodes, treatment given (including dialysis), intensity, and rejection outcome will be included in the listing of renal transplant rejection history.
- Number and percentage of subjects with declining allograft function (following revaccination, HZ episode, and allograft rejection), as determined by serum creatinine measurements. Serum creatinine values will be summarized descriptively. See Section 4.5.3.1 for more details. Allograft dysfunction is defined as having a fold increase in serum creatinine of 1.2 or greater from the reference timepoint.

The listings will contain all events (HZ episodes, rejections) and columns will be included to indicate timing (up to Day 1, Before revaccination, et.)

CC1

CCI

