1.2. Study Design

This study will evaluate the persistence of gE-specific immunogenicity after the primary 2-dose HZ/su vaccination in study ZOSTER-041 and the effect on immunogenicity and safety of revaccination with two additional doses of HZ/su vaccine after approximately 7 years in ZOSTER-041 in renal transplant (RT) subjects taking daily chronic immunosuppressive (CIS) therapy. Former study ZOSTER-041 subjects who received two doses of HZ/su vaccine were offered enrollment into study ZOSTER-073 at participating centers.

This study has three distinct phases:

- In the long-term follow-up (LTFU) phase, subjects will be followed for two years* (Day 1 to Month 24) in ZOSTER-073 study, which is approximately 4-7 years since primary vaccination in ZOSTER-041 study. Over the same time period, the occurrence of confirmed HZ cases and biopsy-proven RT rejections will be prospectively collected. Whereas the occurrence of confirmed/suspected HZ cases; and RT rejections, during the gap between studies ZOSTER-041 and ZOSTER-073, will be retrospectively collected back to subjects' study ZOSTER-041 last visit.

** Subjects who are ineligible for revaccination or unwilling to receive revaccination (hereafter referred to as non-revaccinated subjects) will be invited to be followed in an extension of the LTFU phase for a total of 4 years (Day 1 to Month 49) in ZOSTER-073 study, which is approximately 8-11 years since primary vaccination series in ZOSTER-041 study, with safety and immunogenicity assessments at study Months 37 and 49.*

- In the revaccination active phase (study Months 24 through 26), subjects will receive two additional doses of HZ/su vaccine, administered on a 1 to 2-month apart schedule at study Months 24 and 25. Safety and immunogenicity assessments will be performed 1 month post-revaccination Doses 1 and 2 at study Months 25 and 26, respectively.
- In the revaccination follow-up phase (study Month 26 to study end), safety and immunogenicity following revaccination will be prospectively monitored at study Months 37 and 49 (i.e., 12 and 24 months post-revaccination Dose 2).

Overview of Study Design

HZ/su = Herpes zoster subunit; LTFU = Long-term follow-up; Vacc 1-2 = Vaccination dose 1 & 2; re-Vacc 1-2 = Revaccinations dose 1 & 2

*The second dose of revaccination (Visit 4, study Month 25) will be administered 1 to 2 months after the first revaccination dose.

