**Visit 5 (study Month 26), Visit 6 (study Month 37) and Visit 7 (study Month 49) will occur 1, 12 and 24 months after the second revaccination, respectively.

\$Phone contact will occur about 35 days before Visit 3 (study Month 24) to remind female subjects of childbearing potential to use adequate contraception.

Overview of Study Design Key Features

Design Features	
• Type of study: extension of other protocol(s); ZOSTER-041 for the analysis of long-term immunogenicity and safety.• Experimental design: Phase IIIB, open-label, uncontrolled, multi-centric, single group study.• Duration of the study: The study duration per subject will be approximately 49 months.
– Epoch 001: LTFU phase starting at Visit 1 (Day 1) and ending at Visit 3 (study Month 24)– Epoch 002: Revaccination phase starting at Visit 3 (study Month 24) and ending at Visit 7 (study Month 49)• Primary completion Date (PCD): Visit 5 (study Month 26). The date that the final subject was examined or received an intervention for the purpose of final collection of data for all primary outcomes, whether the clinical trial was concluded according to the pre-specified protocol or was terminated• End of Study (EoS): Last testing results released of samples collected up to Visit 7 (study Month 49).• Study group:
------------------------	---

Table 1 Study group, treatment, and epochs in the study

Study groups*	Target Number of subjects	Actual Number of subjects	Age (Min-Max)**	Treatment name	Epochs	
					From ZOSTER-041 primary study	Epoch 001 (open)
HZ/su	86	68	20 years - 82 years	HZ/su	•	•

HZ/su = Herpes Zoster subunit vaccine.

*HZ/su Group name for subjects who were vaccinated with 2 doses of HZ/su in study ZOSTER 041.

**Age at the first vaccination in study ZOSTER-041.

- **Control:** uncontrolled.
- **Revaccination schedule:** Subjects will receive two additional doses of the HZ/su vaccine, at Visit 3 (study Month 24) and at Visit 4 (study Month 25) in the revaccination phase.
- **Treatment allocation:** All eligible subjects will be enrolled into HZ/su group.
- **Blinding:** Open-label.
- **Sampling schedule:**
 - Blood samples to assess humoral immunogenicity will be collected from all subjects at Visit 1 (Day 1), Visit 2 (study Month 12), Visit 3 (study Month 24), Visit 4 (study Month 25)*, Visit 5 (study Month 26)*, Visit 6 (study Month 37) and Visit 7 (study Month 49).

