3. ANALYSIS SETS

Analysis Set	Description
Enrolled Set	All subjects with a complete vaccination course (2 doses of HZ/su vaccine) in study ZOSTER-041 who met the eligibility criteria and signed informed consent in the study ZOSTER-073.
Per Protocol Set (PPS) for analysis of persistence (LTFU phase from Visit 1 to Visit 3 for all subjects, and at Visit 6 and Visit 7 for non-revaccinated subjects)	The PPS for analysis of persistence will include evaluable subjects (i.e. those meeting all eligibility criteria, complying with the procedures and intervals defined in the protocol, with no elimination criteria) from the Enrolled Set for whom any persistence immunogenicity endpoints measures after primary vaccination course are available from Visit 1 (Day 1) to Visit 3 (study Month 24) regardless of revaccination status and at Visit 6 (study Month 37) and/or Visit 7 (study Month 49) for non-revaccinated subjects.
Exposed Set (ES) for revaccination phase	The ES for analysis of safety will include all subjects with at least one HZ/su vaccine dose administered in the study ZOSTER-073.
PPS for Immunogenicity after revaccination course (revaccination active phase)	The PPS for analysis of immunogenicity after revaccination will be defined by time-point and will include evaluable subjects (i.e. those meeting all eligibility criteria, complying with the procedures and intervals defined in the protocol, with no elimination criteria) from the ES for revaccination who have received 1 or 2 doses of revaccination up to the time point considered from Visit 3 (study Month 24) to Visit 5 (study Month 26) (i.e. 1 dose for Visit 4 and 2 doses for Visit 5) and have any immunogenicity endpoint measures available.
PPS for persistence after revaccination course (revaccination follow-up phase)	The PPS for persistence for analysis of immunogenicity after revaccination will include evaluable subjects (i.e. those meeting all eligibility criteria, complying with the procedures and intervals defined in the protocol, with no elimination criteria) from the ES for revaccination who received 2 doses of revaccination for whom persistence immunogenicity endpoints measures after revaccination course are available with any immunogenicity endpoint measures available from Visit 6 (study Month 37) to Visit 7 (study Month 49).

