4. STATISTICAL ANALYSES

4.1. General Considerations

4.1.1. General Methodology

Confidence intervals (CIs) will use 95% confidence levels unless otherwise specified.

The exact confidence intervals around within-group proportions are derived using the method of Clopper and Pearson [[Clopper](#), 1934].

Unless otherwise specified, continuous data will be summarized using descriptive statistics: n, mean, standard deviation (std), median, minimum, and maximum. Categorical data will be summarized as the number and percentage of subjects in each category.

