6.2.4. Attributing events to vaccine doses

The dose relative to an event is the most recent vaccine dose given to a subject prior to the start of a given event. For example, if the start date of an adverse event is between Dose 1 and Dose 2, the relative dose will be Dose 1.

If an event starts on the same day as a study dose, the relative dose will be derived from the additional information provided in the case report form (CRF) using the contents of the flag indicating if the event occurred before or after study dose. If 'after vaccination' is selected, the relative dose for the event will be the one administered on the start day of the event. If 'vaccination' is selected, the relative dose for the event will be the dose prior to this one.

The number of doses is the number of times the vaccine was administered to a subject

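### The exact 95% CI on the percentage of doses followed by unsolicited AEs makes no allowance for two doses per subject, and is too narrow for common events if a subject's doses are positively correlated

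*SAP*

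**What the plan says.** SAP section 4.3.2.2 plans the number and percentage of subjects with unsolicited AEs in the 30 days after revaccination, by SOC and PT, with exact CIs. A sub-bullet then adds a second output: "The number and percentage doses followed by unsolicited AEs during the 30-day follow-up period with its exact 95% CI".

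Four other places fix how that output would be built.

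- SAP 4.1.1, on the method: "The exact confidence intervals around within-group proportions are derived using the method of Clopper and Pearson". No other exact method for a proportion is given.
- SAP 6.2.4, on counting: "The number of doses is the number of times the vaccine was administered to a subject".
- SAP 1.2, on the schedule: "subjects will receive two additional doses of HZ/su vaccine, administered on a 1 to 2-month apart schedule".
- SAP section 3, on the population: "The ES for analysis of safety will include all subjects with at least one HZ/su vaccine dose administered in the study ZOSTER-073".

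Protocol section 10.3.4 plans only subject-level percentages for unsolicited AEs. The dose-level line is therefore an addition made in the SAP, and SAP 4.8 (Changes to Protocol Defined Analyses) does not list it. The SAP version history records that dose-level SAE summaries were removed because SAEs cannot be attributed to a dose. Neither document mentions within-subject correlation for the dose-level line that remains.

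**The concern.** A Clopper-Pearson interval inverts the binomial distribution, so its coverage guarantee requires the counted units to be independent. Here the unit is the dose, and a subject who completes revaccination enters the denominator twice, 1 to 2 months apart. The same transplant recipient, on the same background immunosuppression and filling in the same kind of diary, may well report similarly after both doses. If so, the doses carry less information than their number suggests, and the table overstates the precision of the dose-level rate.

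What is at stake is limited. The study is uncontrolled and descriptive, so estimates and intervals are what the reader has to go on, and an interval labelled exact 95% should cover about 95% of the time. SAP 4.3.2 also repeats unsolicited AE analyses by age stratum, so the same construction may recur there.

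**Working it through.** **No figure in the plan to reproduce.** The documents give no numerical value for this interval, no expected AE rate and no within-subject correlation.

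**Inputs from the documents.** Two doses per fully revaccinated subject; two-sided 95% level; 68 subjects actually enrolled (SAP 1.2, Table 1). The number revaccinated is not stated, so 68 subjects and 2 × 68 = 136 doses are ceilings.

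**Assumptions.**
- Number of subjects with two doses, m = 58 or 68. The lower value is 68 × 0.85 = 57.8. It borrows the plan's 15% loss rate, which was set for immunogenicity evaluability, and serves only as an illustration.
- Per-dose AE rate p = 10-50% for common events, 1-2% for rare terms.
- Within-subject correlation ρ = 0 to 0.7.

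**Step 1: variance.** For clusters of two, the variance of the pooled percentage is p(1−p)(1+ρ)/(2m). The design effect is 1+ρ, and the standard error grows by √(1+ρ): 1.05 at ρ = 0.1, 1.10 at 0.2, 1.14 at 0.3, 1.22 at 0.5 and 1.30 at 0.7.

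**Step 2: exact coverage of the planned interval.** For one subject:

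- P(AE after both doses) = p² + ρp(1−p)
- P(AE after exactly one) = 2p(1−p)(1−ρ)
- P(AE after neither) = (1−p)² + ρp(1−p)

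Convolving m such distributions gives the distribution of the total count. Summing it over counts whose Clopper-Pearson interval on 2m doses contains p gives the coverage. Ranges are over m = 58 and 68 and p = 10, 20, 30, 40 and 50%:

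| ρ | Coverage (%) |
|---|---|
| 0 | 95.1-96.9 |
| 0.1 | 93.9-96.1 |
| 0.2 | 92.8-95.2 |
| 0.3 | 91.6-94.2 |
| 0.5 | 89.2-92.2 |
| 0.7 | 86.8-90.1 |

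In this range, coverage is below 95% in every scenario from ρ = 0.3 upward. At 0.1 and 0.2 the conservatism built into Clopper-Pearson absorbs much of the effect.

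**Step 3: rare terms.** For p = 1-2% and the same m, coverage is 96.4-98.4% at ρ = 0.3 and 95.4-97.9% at ρ = 0.5. There is no shortfall.

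**Step 4: what the reader would see.** Take the ceiling of 136 doses and suppose 41 (30%) are followed by an AE. The planned interval is 22.6-38.6%, a width of 16.0 points. Clopper-Pearson on the effective number of doses, 136/(1+ρ), gives:

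| ρ | Effective doses | Interval (%) | Width (points) |
|---|---|---|---|
| 0.1 | 123.6 | 22.2-39.0 | 16.8 |
| 0.3 | 104.6 | 21.6-39.9 | 18.3 |
| 0.5 | 90.7 | 20.9-40.7 | 19.7 |
| 0.7 | 80.0 | 20.4-41.4 | 21.0 |

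At ρ = 0.5 each limit moves by about two percentage points.

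**The case against.** **The direction is conditional.** A reader might infer that the interval is certainly too narrow, or invalid throughout the table. The documents do not support that. They give no correlation; at zero or below, the interval is not too narrow, and at 0.1 to 0.2 coverage stays close to 95%. This part of the objection stands: positive correlation is plausible, but it is an assumption.

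**Most rows may be rare events.** If the dose-level output follows the SOC and PT layout of its parent bullet, many terms may have very low rates, where step 3 shows no under-coverage. This also stands. The problem is confined to the any-AE row and common terms.

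**Pooling is inferred.** The SAP does not say whether Dose 1 and Dose 2 are combined. A table split by dose would have one unit per subject and no difficulty. However, where section 4.3.2.2 wants results by dose it says so, in its first bullet, and this line does not. A split by dose would also merely count subjects, so pooling remains the natural reading.

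**It is only descriptive.** SAP 2.1 rules out hypothesis testing, and the row supplements subject-level results. That makes the consequence small, but it does not justify calling an interval exact when its independence assumption has been set aside.

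**Some remedies work poorly.** An effective sample size needs a correlation that the documents lack and sparse terms cannot estimate well. Robust variance breaks down at zero counts and is unreliable with one or two events. This stands, and it limits the fix.

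**Conclusion.** The mismatch is in the text: a binomial interval is planned on doses, with up to two per subject and no allowance for clustering. That it makes the interval too narrow depends on positive within-subject correlation. With the subject numbers and common-event rates assumed above, the loss of coverage is slight at a correlation of 0.1 to 0.2, and coverage is about 89-92% at 0.5 and 87-90% at 0.7. Terms at 1-2% are not affected up to 0.5.

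A reader might take this as a doubt about the unsolicited AE results in general. It is not one. The dose-level percentage itself is unchanged, the subject-level percentages and their exact CIs are sound, and no test or decision in the plan rests on this row. The point is minor, but worth correcting because doing so is easy.

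**What to change.** In SAP 4.3.2.2, change the sub-bullet so that the dose-level number and percentage are reported without a CI, and keep Clopper-Pearson for subject-level percentages. This breaks no protocol commitment, because the protocol plans only the subject-level figures.

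If a dose-level interval is wanted, give it for the overall any-AE row only, clustered by subject (for example a bootstrap that resamples subjects, or a cluster-robust interval). Neither needs an assumed correlation. Do not extend it to sparse SOC or PT rows. State in the same sentence that doses are pooled over Dose 1 and Dose 2.

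The cost is one SAP sentence and, if the clustered interval is chosen, some programming. The downside is that the dose-level row loses its interval or shows a slightly wider one.
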